A single cohort of patients will be used for all 3 Aims (i.e. both intervention and control groups recruited into the randomized controlled trial (RCT) will form a single cohort for analyses in Aims 2 and 3). We will enroll 54 patients from all Johns Hopkins Hospital adult ICUs. If patients are lost to follow-up, we will enroll up to 10 additional patients to obtain 12-week outcomes assessments on a total of 54 patients (27 in each group). Oral informed consent will be obtained from all participants.

Aim 1 Methods: We will conduct a single-site, pilot RCT (N=54) evaluating the feasibility (primary objective) and efficacy (secondary objective) of a 12-week behavioral activation-rehabilitation (BA-R) intervention versus “usual care”, in acute respiratory failure (ARF) survivors. We will evaluate the BA-R intervention via an RCT study design, with blinded outcome assessments. We will test the feasibility of this intervention (primary outcome) and its efficacy (secondary outcome) at the end of intervention. Figure 2 shows study timeline.

[figure not shown]
After return home, consented patients will be randomized to: (1) behavioral activation and rehabilitation (BA-R) intervention or usual care. Randomization will occur via web-based tool, using variable-sized

blocks from 2 to 4, and stratified by history of depression prior to ICU admission (based on chart review and patient interview). Baseline variables are detailed in Table 1 below.

Table 1: Baseline Variables

Variable	Collection	Measurement Scale
Patient Variables		
Age/sex/race	Chart review	Continuous/Binary/Categorical
Education (number of years/highest attainment)	Patient interview	Continuous/Categorical
Employment & Health Insurance status	Patient interview	Categorical
Comorbidity indices: Charlson (CCI) ^a & Functional (FCI) ^b	Chart review	Ordinal
Alcohol intake/misuse / Drug abuse	Chart review	Categorical
Physical function at baseline: AMPAC-CAT ^{87,88 c}	Patient interview	Continuous
ICU and Hospital Variables		
ICU admission diagnosis (e.g., sepsis, renal failure)	Chart review	Categorical
Severity of illness: APACHE II ^d	Chart review	Continuous
Benzodiazepine use and dosing ^{56,89,90}	Chart review	Continuous
Daily ICU Sedation Status: RASS ⁹¹	Chart review	Ordinal
Daily ICU Delirium Status: CAM-ICU ^{92,93}	Chart review	Categorical
Daily Minimum Glucose ⁹⁰	Chart review	Continuous
ICU and Hospital Length of Stay	Chart review	Continuous

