Participants cannot be blinded to the intervention. Treatment allocation will be concealed, except to staff performing the intervention. Research staff performing all outcome assessments will be blinded (except [name] who will not be masked to treatment assignment and will administer the SCID). Patients will be instructed (using standard language, as per prior research)¹⁰¹⁻¹⁰³ not to discuss treatment allocation with staff prior to each assessment. Adequacy of blinding will be assessed by asking assessors to indicate if they were un-blinded and for their “best guess” of patients’ treatment allocation.¹⁰³

d. Justification of why participants will not receive routine care or will have current therapy stopped.

All study participants in the usual care group will receive routine care. Participants in the intervention group will receive the intervention in addition to routine care.

e. Justification for inclusion of a placebo or non-treatment group.

We chose to compare our intervention against a “usual care”, rather than a sham control that would attempt to control for extra attention but does not represent real-world usual care. We will measure usual care for both control and intervention groups (Table 2). Participants in the usual care group will not be deprived of any known potential benefits by not being included in the intervention group (no proven benefit yet in the ARF population).

f. Definition of treatment failure or participant removal criteria.

Participants will only be removed from the study if they withdraw consent.

g. Description of what happens to participants receiving therapy when study ends or if a participant’s participation in the study ends prematurely.

If a participation in the study ends prematurely, the participant will continue to receive usual care. Ending the intervention prematurely does not pose any harm to the participant.

5. Inclusion/Exclusion Criteria

Table 3. Eligibility Criteria

Inclusion Criteria:

≥18 years old

Living at home before the current admission (not in a facility)

Acute respiratory failure managed in the ICU ≥ 24hrs (≥1 of the following):

- 1) Mechanical ventilation via an endotracheal tube or tracheostomy > 12hrs (and not ventilator-dependent before admission) OR
- 2) Non-invasive ventilation (CPAP, BiPAP) > 4 hours in a 24 hour period provided for acute respiratory failure (not for OSA or other stable use) OR
- 3) High flow nasal cannula with FiO₂ ≥ 0.5 for ≥4 hours in a 24hr period

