c. Statistical plan including sample size justification and interim data analysis.

Sample Size: As a pilot RCT, we aim to enroll a convenience sample of ~1.5 patients/month, for a total of 54 patients (based on 36 months of recruitment; see Timeline-Candidate Statement). Extensive experience enrolling ARF patients in prior studies by our group^{10,121,125-127} suggests this rate is feasible for a K-23 award at this study site. We expect an overall <15% missing completion rate due to mortality and loss to follow-up (in our prior study of >500 ARF survivors, loss to follow-up was 2% with 7% mortality at 6 months¹²⁵), thus, we expect 54 patients to complete the intervention. With 54 participants (27 in each group), assuming 5% alpha, 80% power and HAD SD of 4.2 points based on our prior research in ARF survivors^{89,90}, for our secondary aim of efficacy, we can detect a 3.1 point difference in HADS score between the 2 treatment groups, which approximates HAD's 2.9 point minimum important difference (MID) in ARF survivors.¹²⁸ This proposed enrollment rate and sample size is consistent with existing pilot/feasibility trials in ARF research.^{101,129,130}

Statistical Analysis

Hypothesis 1a: *A 12-week BA-R intervention in ARF survivors will be feasible, as demonstrated by an average accrual rate of 1.5 patients per month, completion of ≥80% of the intervention phone calls, and ≤15% of enrolled patients lost to follow-up for outcomes assessments at end of the 12-week intervention.* We will assess the total number of intervention phone calls completed per patient as a proportion of the number of intervention phone calls each patient is intended to complete (i.e., 9 intervention calls – weekly during first 6 weeks and bi-weekly for second 6 weeks of the 12-week protocol). We also will assess total number of intervention phone calls completed by all study participants as a proportion of total intervention phone calls expected in the study. We will calculate the number of patients completing the 12-month follow-up session as a proportion of the number of patients enrolled to measure loss to follow-up.

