Hypothesis 1b: *At the end of the 12-week BA-R intervention, ARF survivors in the BA-R versus “usual care” group will demonstrate decreased depressive symptoms, less impairments in physical function and quality of life, and reduced healthcare utilization.* Analyses will follow a modified intention-to-treat principle and a 2-tailed p<0.05 is statistically significant. Patient mortality is expected to occur infrequently (see Sample Size above) and not to differ by treatment vs. control group; therefore, all analyses will be conducted for 12-week survivors only. The analysis will include separate comparisons of the effect of the BA-R intervention vs usual care control on each of the blinded outcomes in Table 4. These analyses will estimate the average treatment effect, i.e. the difference in the mean 12-week outcome comparing the BA-R intervention to the usual care control, using the precise locally efficient augmented simple estimator (PLEASE) described in Colantuoni and Rosenblum[REF: 135]. This method for estimating the average

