Hypothesis 1c: We will conduct qualitative research, using thematic analysis, to identify key barriers and facilitators to engaging with the BA-R intervention, as well as perceived satisfaction, acceptability and feasibility of BA-R. All interviews will be audio recorded using a digital recorder and subsequently transcribed on a rolling basis. Using a data-driven approach, the first five interviews and associated interviewer field notes will be independently read by [name] and a second coder with expertise in qualitative research methods. The data will be segmented by identifying information pertinent to the research question then categorizing and giving identifying names (codes) to the patterns that emerge. Following the review of the five initial interviews, the two investigators will meet to discuss common findings and key themes. A code book will then be developed to guide the analysis of the transcripts through an iterative process of discussion and review. Transcripts will be reviewed on an ongoing basis to identify when thematic saturation is reached, defined by at least 3 interviews without additional information. Nvivo software will be used to organize the data for analysis. Coding will be compared

between the coders using percentage agreement and Cohen's kappa coefficient. Discrepancies will be reviewed and resolved through discussion between reviewers and a third review, if needed.

Hypothesis 2a: *Increased resilience, adaptive coping, and social engagement are associated with fewer depressive symptoms using the combined patient cohort from the BA-R and control groups in Aim 1.* Our primary outcome is depressive symptoms from the Hospital Anxiety and Depression Scale (HADS). First, descriptive statistics (i.e. mean, standard deviation, histograms) will be performed for the baseline HADS and the exposure and confounding variables. Next, a bi-variable analysis will be conducted for the HADS vs the baseline exposure variables for Aim 1 (i.e., CD-RISC 10, Brief COPE, BADS) using linear regression. In multivariable analyses, we also will include potential confounding variables (Table 1), including no more than 4 covariates in each model to avoid overfitting with sample size 54 (after accounting for mortality and loss to follow-up). These analyses will be conducted for all patients in the combined cohort in Aim 1.

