Hypothesis 2b: *At the end of the 12-week intervention, ARF survivors in the BA-R versus “usual care” control group will demonstrate improvements in coping, resilience and social engagement.* Analyses for the comparison between the intervention and usual care groups will follow a modified intention-to-treat principle, with a 2-tailed $p < 0.05$ is considered significant. Analysis will include separate comparisons of the intervention vs control for each of outcomes (Brief Cope, CD RISC, BADS), in accordance with the description above for Hypothesis 1b.

Hypothesis 2c: *We will conduct qualitative research, using thematic analysis, to identify the role of resilience, coping, and social engagement in recovery from ARF.* See analysis plan above for Hypothesis 1c. This analysis will include all patients in the combined cohort from Aim 1.

Hypothesis 3: *The HADS and PHQ-8 will adequately discriminate depressive symptom severity vs. the SCID-5 “gold standard” using the combined patient cohort from the BA-R and control groups in Aim 1.* All analyses will be conducted using only the 12-week outcomes data. The RCT inclusion criteria (in Aim 1), which establish the patient cohort for Aim 3, include only patients with PHQ-2 ≥ 2 (i.e., at least mild depressive symptoms). Therefore, for Aim 3 analyses, we will categorize depressive symptoms based on severity category for the SCID-5 (mild vs moderate to severe). We will then examine the screening characteristics of HADS and PHQ8 total scores vs the SCID-5 using a receiver operating characteristics (ROC) curve, including the area under the ROC curve (AUC), and sensitivities, specificities, and positive and negative predictive values at each HADS and PHQ8 total-score cut point. Our sample size (N=54 patients) is adequate to permit an assessment of criterion validity that is rated, at least, as “good” quality according to the COSMIN standard for psychometric analyses.¹³¹ In addition to assessment of criterion validity, we will assess internal consistency of the PHQ-8 using Chronbach’s alpha, with a result of ≥ 0.7 and < 0.95 indicating “good” quality as per COSMIN¹³² (HADS has an existing publication demonstrating good internal consistency in ARF survivors so no such analysis will be repeated for HADS)¹³³.

d. Early stopping rules.

There will be no interim analyses to determine early stopping for efficacy or futility with respect to the main efficacy hypothesis. The primary outcome for this study is feasibility.

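### HADS sizes the efficacy aim but is never named as the lead outcome for Hypothesis 1b; about 12 blinded outcomes are each tested at unadjusted p<0.05

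*Combined protocol and SAP*

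**What the plan says.** The trial is described in section 4a as "evaluating the feasibility (primary objective) and efficacy (secondary objective"), so efficacy ranks second but is a stated objective.

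Section 7c, Sample Size, ties that objective to one outcome: "for our secondary aim of efficacy, we can detect a 3.1 point difference in HADS score between the 2 treatment groups". No other outcome has a power statement.

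Section 7c, Hypothesis 1b, does not carry this priority into the analysis. It states that "a 2-tailed p<0.05 is statistically significant" and plans "separate comparisons of the effect of the BA-R intervention vs usual care control on each of the blinded outcomes in Table 4". Hypothesis 2b applies the same threshold to "separate comparisons of the intervention vs control for each of outcomes (Brief Cope, CD RISC, BADS"), three outcomes that are also in Table 4.

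Two other statements limit what can be tested. Section 4c exempts the SCID assessor from blinding, "who will not be masked to treatment assignment and will administer the SCID", so SCID-5 is not a blinded outcome. Hypothesis 1b also says that "all analyses will be conducted for 12-week survivors only", so survival status cannot differ between the groups analysed.

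HADS is called primary in one place, under Hypothesis 2a: "Our primary outcome is depressive symptoms from the Hospital Anxiety and Depression Scale (HADS"). That label belongs to the association analysis in the combined cohort, not to the comparison of BA-R with usual care.

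**The concern.** Hypothesis 1b covers depressive symptoms, physical function, quality of life and healthcare utilization. The plan does not say which result decides it. Depressive symptoms have two blinded scales, HADS and PHQ-8, and there is no rule for the case where they disagree. Section 7d refers to a main efficacy hypothesis without saying which outcome it concerns.

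The plan labels some other analyses exploratory or secondary, but gives these comparisons a significance threshold and no such label. With many outcomes each tested at 0.05, an isolated significant result is fairly probable even if BA-R has no effect. Such a result could be singled out afterwards when a larger trial is being justified.

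**Working it through.** **The plan's own figure.** The plan gives no family-wise error rate. The nearest stated figure is the detectable HADS difference: 27 per group, SD 4.2, two-sided 5% alpha, 80% power, giving 3.1 points.

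- Standard error: 4.2 × √(2/27) = 1.143.
- Normal approximation: 1.143 × (1.960 + 0.842) = 3.20 points. The noncentral t gives 3.26.
- Power at 3.1 points is 77.4% (normal) or 75.9% (t).

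The stated 3.1 is therefore slightly optimistic under an unadjusted comparison. This does not affect the multiplicity point. It does confirm that HADS is the outcome the efficacy aim was sized on.

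**Counting the tests.** Table 4 has these blinded lines at the end of the intervention:

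1. HADS
2. PHQ-8
3. AMPAC-CAT
4. Return to baseline work/activity
5. EQ-5D-5L
6. Healthcare utilization (taken as one)
7. Employment status
8. Brief Cope
9. BADS
10. CD RISC
11. MoCA-BLIND
12. IES-R

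SCID-5 is left out because its assessor is unmasked. Survival is left out because only survivors are analysed. The Hypothesis 2b outcomes are lines 8 to 10 and are counted once. Lines 1 to 6 are the ones that fall in the domains Hypothesis 1b names, which gives a narrower family of six.

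**Formulas, with no true effect.**

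- Independent tests, either direction: 1 − 0.95^k. For k = 12, 1 − 0.5404 = 46.0%. For k = 6, 1 − 0.7351 = 26.5%.
- Independent tests, favouring BA-R only: 1 − 0.975^k. For k = 12, 1 − 0.7380 = 26.2%. For k = 6, 1 − 0.8591 = 14.1%.
- Correlated tests: test statistics taken as equicorrelated standard normal with pairwise correlation ρ. Given the shared component x, the tests are independent. The probability that none is significant is then the average over x of p(x)^k. In the either-direction case, p(x) = Φ((1.96 − √ρ·x)/√(1−ρ)) − Φ((−1.96 − √ρ·x)/√(1−ρ)). In the favourable-only case, the second term is dropped.

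| Assumed ρ | 12 tests, either direction | 12 tests, favouring BA-R | 6 tests, either direction | 6 tests, favouring BA-R |
|---|---|---|---|---|
| 0 | 46.0% | 26.2% | 26.5% | 14.1% |
| 0.3 | 39.7% | 20.2% | 24.1% | 12.2% |
| 0.5 | 31.9% | 16.0% | 20.7% | 10.4% |
| 0.7 | 23.2% | 11.6% | 16.4% | 8.2% |

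A simulation with 27 per arm, 12 outcomes and ρ = 0.5 gave 32.3% in either direction and 16.3% favouring BA-R, in line with the table.

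**Sensitivity.** At ρ = 0.8, 12 tests give 18.6% and 9.3%. If subscales and utilization components were tested separately, the count would rise. With 16 tests, the either-direction figure is 56.0% if independent and 37.4% at ρ = 0.5. For one named test, the benchmarks are 5% in either direction and 2.5% favouring BA-R.

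**The case against.** The strongest reply is that HADS is already the lead in all but name. It is the only outcome with a power calculation, depressive symptoms come first in Hypothesis 1b, and HADS (not PHQ-8) is the depression scale in the baseline battery and the drop-out model. PHQ-8 enters mainly as an instrument to be validated under Aim 3. This stands as a reading of intent, so it would be wrong to say the plan has no efficacy focus. What is missing is the sentence in the analysis text that gives HADS priority.

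The second reply is that a family of 12 pools two aims. Brief Cope, BADS and CD RISC serve Hypothesis 2b, and employment, MoCA-BLIND and IES-R lie outside the domains of Hypothesis 1b. This stands in part. The Hypothesis 1b text does send every blinded Table 4 outcome to testing, but the six-outcome figures are the fair ones for the hypothesis as worded, and they are shown alongside.

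The third reply is that this is a pilot. Feasibility is primary, the Hypothesis 1b analysis is framed as estimating an average treatment effect, and unadjusted secondary comparisons are common at this stage. This limits the consequence. It does not remove the point, because the plan declares a significance threshold and does not label these comparisons exploratory.

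Two stronger readings are tempting and are not supported. A reader might infer that one p<0.05 anywhere would establish efficacy. No text says so: the threshold is defined per comparison, and Hypothesis 1b is worded as a conjunction of domains. A reader might also infer that the pilot is likely to show a false benefit. Even the largest either-direction figure for 12 tests, 46.0%, is below one half, and the chance of a false result in favour of BA-R is about half the either-direction figure.

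**Conclusion.** The point holds as a gap between the sizing and the analysis. The efficacy aim is sized on HADS, but the analysis gives HADS no priority, does not choose between HADS and PHQ-8, and tests about 12 outcomes at unadjusted two-tailed 0.05.

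With no true effect, the chance of at least one significant difference in either direction is about 23% to 46%, and of at least one favouring BA-R about 12% to 26%. For the six Hypothesis 1b outcomes the ranges are 16.4% to 26.5% and 8.2% to 14.1%. Each range runs from an assumed common correlation of 0.7 down to 0. The outcome counts are my reading of Table 4, and the documents give no correlations. The primary feasibility conclusion is unaffected, so this is a worthwhile clarification of modest weight.

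**What to change.** In section 7c, Hypothesis 1b, name the 12-week HADS depression score as the single efficacy comparison tested at two-sided 0.05, and limit the significance sentence to it. State that all other Table 4 comparisons, including PHQ-8 and the three Hypothesis 2b outcomes, are exploratory and will be reported as PLEASE estimates with 95% confidence intervals and no significance claim. Amend the matching sentence under Hypothesis 2b.

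The efficacy error rate then returns to 5%, and the choice between HADS and PHQ-8 is settled before the data are seen. The cost is a few sentences, with no new data or method. The downside is that no formal significance claim can be made for the other outcomes, none of which has a power statement.

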Health Care Utilization and Estimated Costs	Admission to hospital, nursing & rehabilitation facilities; plus mental health & physical rehab utilization (8 min)			x
Survival status	Patient/Proxy (<1 min)			x
Coping Style	Brief Cope (28 items; 10 min)	x		x
Social Engagement	BADS (25 items; 5 min)	x		x
Resilience	CD RISC (25 items; 10 min)	x		x
Cognitive Function	MoCA-BLIND (8 questions; 5 min)			x
PTSD	IES-R (22 items; 6 min)			x

Abbreviations: HADS= Hospital Anxiety and Depression Scale, SCID-5= Structured Clinical Interview for DSM-5 (Mood Disorders Section only), AMPAC-CAT= Activity Measure for Post-Acute Care--Computer Adaptive Test, BADS= Behavioral Activation for Depression Scale, CD RISC= Connor-Davidson Resilience Scale

a: semi-structured interview

Brief Cope: Coping strategies will be assessed using the self-reported 28-item Brief Cope Scale.⁹⁴ The scale is a valid and reliable, used in medical populations, with strong measurement properties.^{94,120,122} It will assess active (e.g. problem solving) versus avoidant coping (e.g., behavioral disengagement, self-blame).

Behavioral Activation for Depression (BAD) Scale: This 25-point scale⁹⁵ assesses social engagement and other aspects of behavioral activation. We demonstrated BADS's validity in medical populations with depressive symptoms and its sensitivity to change with depression treatment.¹⁶

Connor-Davidson Resilience Scale (CD RISC): This 25-item scale⁹⁶ assesses resilience. It has been validated in a variety of patient populations and specifically used in research involving ARF survivors.^{102,105,106}

Adherence to the BA-R Intervention: will be evaluated as done in prior studies^{83,85} by: (1) measuring the number of phone attempts needed by the OT to reach the participant for each session, and (2) calculating the proportion of sessions fully completed (with sub-analysis for number partially completed).

Montreal Cognitive Assessment (MoCA) – BLIND: is a validated phone-based version of the original MoCA,¹²³ a rapid screening instrument for mild cognitive dysfunction. The MoCA - BLIND assesses different cognitive domains including attention and concentration, memory, language, conceptual thinking, calculation and orientation. It will take 5 minutes to administer the MoCA-BLIND.

Impact of Events Scale – Revised (IES-R): This is the most commonly used instrument for assessing PTSD symptoms in ARF survivors.¹⁰⁷ It has 22 items, is reliable and valid.¹²⁴

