treatment effect is similar to the analysis of covariance (ANCOVA) approach in that it incorporates the baseline outcome (if measured) which, if correlated with the 12-week outcome, can improve the precision of the estimated average treatment effect [Ref 134]. This method also accounts for more general patient drop-out models than the ANCOVA approach. Specifically, the ANCOVA approach is valid under completely at random drop-out, whereas the PLEASE is valid under missing at random drop-out, i.e. when patient drop-out differs by treatment group or across levels of the baseline outcome or other measured variables at baseline. The PLEASE requires a priori specification of three models: an outcome regression model (fit separately for each treatment group) that will include age, gender and the baseline outcome (if measured), a propensity score model that will include age, gender and the baseline outcome (if measured) and a drop-out model (fit separately for each treatment group) that will include age, gender, and the outcomes measured at baseline (HADS, Brief Cope, CD RISC, BADS). As exploratory analyses, the 12-week outcomes (e.g. HADS scores) will be summarized (summary statistics including counts of missing values and histograms) and the correlation of the baseline (if appropriate) and 12-week outcomes will be computed, separately by treatment arm. Patient mortality, drop-out and missing data will be described for all variables, separately for treatment vs control groups. Patient characteristics will be compared between those with vs. without missing outcomes (due to drop-out and missing values).¹³⁶⁻¹³⁸

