A series of secondary analyses will be conducted to improve our understanding of the changes in the outcomes over time under the BA-R intervention and usual care control and to improve the design of subsequent larger randomized trials evaluating the effect of the BA-R intervention. Specifically, the outcomes over time within each treatment group will be visualized using spaghetti plots to display each patient's data with the mean outcome over time trajectory over time highlighted. Longitudinal linear regression models for the longitudinal outcomes (i.e. baseline, 6-week and 12-week outcomes) will be constructed that account for time (factor), treatment and the interaction of treatment and time. These longitudinal models will be fit using weighted least squares and will allow for the possibility that the variance in the outcomes can change over time and that outcomes measured on the same patient over time may be correlated. In addition, we will explore the prognostic ability of other baseline variables (e.g. age, sex and history of depression) for the 12-week outcomes using the method described by Colantuoni and Rosenblum.¹³⁵ Specifically, we will compute the leave-one-out cross-validated relative R-square which compares the R-square obtained when modeling the 12-week outcomes as a function of selected baseline variables, separately for each treatment arm, to that obtained by predicting the 12-week outcomes with the treatment arm specific mean. The statistic ($1 - 1/\text{relative R-square}$) is roughly the sample size reduction that can be achieved if the selected baseline variables are incorporated into an adjusted treatment effect estimator compared to using an unadjusted estimator. This assessment will provide relevant information to improve the design and analysis of subsequent larger randomized trials evaluating the effect of the BA-R intervention; specifically, by informing which additional prognostic baseline variables to include in the ANCOVA approach described above to further improve the precision of the estimated treatment effects.

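### The PLEASE outcome and propensity models omit the randomisation stratum (history of depression): a small, cheap correction to secondary efficacy intervals, to be made only with a small-sample-corrected standard error

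*Combined protocol and SAP*

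**What the plan says.** - **Randomisation** (Section 4a, Aim 1 Methods): web-based, in variable blocks of 2 to 4, "stratified by history of depression prior to ICU admission". This is the only stratification factor.
- **Estimator** (Section 7c, Hypothesis 1b): each 12-week comparison is made "using the precise locally efficient augmented simple estimator (PLEASE) described in" a cited methods paper, with two-tailed p<0.05. The section states no standard error, interval method or small-sample correction. The cited paper is not available here.
- **Pre-specified outcome model** (same section): "an outcome regression model (fit separately for each treatment group) that will include age, gender and the baseline outcome (if measured").
- **Pre-specified model for treatment assignment** (same section): "a propensity score model that will include age, gender and the baseline outcome (if measured").
- **Pre-specified drop-out model** (same section): also fitted per arm, it holds the two demographic covariates plus "the outcomes measured at baseline (HADS, Brief Cope, CD RISC, BADS"). History of depression is in none of the three models. Hypothesis 2b refers back to this description.
- **Only analysis use of the factor** (Section 7c, secondary analyses): "we will explore the prognostic ability of other baseline variables (e.g. age, sex and history of depression"), to inform later trials.
- **Outcomes with no baseline value** (Section 7b, Table 4; Table 1): EQ-5D-5L, IES-R and "MoCA-BLIND (8 questions; 5 min") are collected at the end of the intervention. PHQ-8 is neither in Table 1 nor in the Hypothesis 1b list of baseline outcomes, although its row in Table 4 is hard to read in the supplied text. For these outcomes the first two models hold age and gender only.
- **Numbers** (Section 4a, Overview): "we will enroll up to 10 additional patients to obtain 12-week outcomes assessments on a total of 54 patients", 27 per arm.

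**The concern.** Stratifying on a prognostic factor removes its contribution to the between-arm variance. An analysis that leaves the factor out, with a standard error that does not know about the strata, still counts that contribution as noise. The reported interval is then wider than the true uncertainty, and the test is conservative. The plan judged history of depression important enough to stratify on, but does not say why the analysis drops it. Its place on the exploratory list is no explanation, because age and sex are on that list too and are in the models.

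At stake are the intervals and p-values for the secondary efficacy outcomes, which are meant to help design a larger trial. HADS has a baseline score that can absorb much of what history predicts. Outcomes with no baseline measure are more exposed.

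**Working it through.** **The plan's own figure.** The plan gives no figure on this point. Its one efficacy calculation is a detectable HADS difference of 3.1 points (27 per arm, SD 4.2, two-sided 5%, 80% power). Recomputed: (1.960 + 0.842) × 4.2 × √(2/27) = 3.20. That gap is a separate matter. Below, 3.1/4.2 = 0.738 SD serves only as an effect size for power.

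**Inputs from the documents:** 54 observed outcomes, 27 per arm, blocks of 2 and 4 within two strata, the covariate lists above, two-sided 5%.

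**Assumed, not in the documents:** 40% with history; within-stratum baseline/12-week correlation 0.5; history effect h = 0, 0.3, 0.6 or 1.0 SD; age and gender not prognostic; a standard error that ignores the strata.

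**Step 1, large-sample size.** Let q = 0.4 × 0.6 = 0.24 and the within-stratum variance be 1.

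- *No baseline measure.* Residual variance is 1 + h²q without the stratum and 1 with it. The width ratio is √(1 + h²q). At h = 0.6: √(1 + 0.36 × 0.24) = √1.0864 = 1.042. At h = 1.0: √1.24 = 1.114.
- *HADS, history shifting both scores by h.* Residual variance without the stratum is (1 + h²q) − (0.5 + h²q)²/(1 + h²q); with it, 1 − 0.5² = 0.75. At h = 0.6: 1.0864 − 0.5864²/1.0864 = 0.770, ratio √(0.770/0.75) = 1.013. At h = 1.0: 1.24 − 0.74²/1.24 = 0.798, ratio 1.032.

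From these, subtract the small-sample cost of the extra parameter, about 0.8% in the simulation.

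**Step 2, simulation at N = 54** (4,000 replicates per scenario). The estimator is a logistic propensity model with inverse-probability-weighted outcome regressions per arm, standardised over all patients. The corrected standard error scales arm residuals by √(n_a/(n_a − p)) and uses t with n − 2p degrees of freedom. The uncorrected one is the influence-function standard error with z.

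| | h = 0 | 0.3 | 0.6 | 1.0 |
|---|---|---|---|---|
| **HADS**: width change from omitting (corrected SE) | -0.8% | -0.5% | +0.6% | +2.3% |
| True SD, omit / include | 0.245 / 0.245 | 0.249 / 0.249 | 0.246 / 0.247 | 0.245 / 0.245 |
| Coverage %, corrected, omit / include | 95.1 / 95.2 | 94.6 / 94.9 | 95.6 / 95.5 | 96.0 / 95.6 |
| Coverage %, uncorrected, omit / include | 92.5 / 92.1 | 91.9 / 91.6 | 92.9 / 91.9 | 93.5 / 92.5 |
| **No baseline measure**: width change | -0.8% | +0.3% | +3.4% | +10.6% |
| True SD, omit / include | 0.279 / 0.279 | 0.283 / 0.283 | 0.280 / 0.280 | 0.280 / 0.279 |
| Coverage %, corrected, omit / include | 95.3 / 95.4 | 95.5 / 95.5 | 96.3 / 95.6 | 97.2 / 95.7 |
| Coverage %, uncorrected, omit / include | 93.2 / 92.8 | 92.6 / 92.1 | 94.0 / 92.9 | 95.7 / 93.3 |

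Step 1 less 0.8% gives about +0.5% and +2.4% for HADS, and +3.4% and +10.6% with no baseline, in line with the table. Repeat runs agree on width to within 0.2 points. Monte Carlo error on coverage is about 0.3 to 0.5 points.

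**Step 3, power** at 0.738 SD with h = 0.6, omit versus include: HADS 83.1% versus 82.8%; no baseline measure 69.2% versus 71.9%.

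**Step 4, sensitivity.**
- *Prevalence 20 / 40 / 50% at h = 0.6:* HADS +0.1 / +0.6 / +0.7%; no baseline +1.9 / +3.4 / +3.6%. At 20%, the 2.8% of samples with a nearly empty stratum were excluded.
- *History acting wholly beyond the baseline HADS score* (30% with history, corrected SE in HADS points, omit / include): 1.018 / 1.021 for a 1-point effect and 1.020 / 0.997 for 2 points, the latter about 2% (1.020/0.997 = 1.023). A 3-point effect gives 1.025 / 0.958, about 7%, but nothing in the documents suggests an effect that large.
- *With drop-out* (60 enrolled, 2.8 to 3.4 lost per arm, six-covariate drop-out model): width changes are nearly the same, -0.7 / -0.4 / +0.7 / +2.5% for HADS and -0.7 / +0.3 / +3.5 / +10.7% with no baseline. Coverage with the stratum is 93.6 to 94.3% corrected and 90.1 to 91.8% uncorrected. Corrected coverage without the stratum was not computed there, so no coverage gain is shown in that setting.

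**The case against.** The strongest reply is that the direction depends on a choice the text does not settle. Conservatism appears only with a standard error that is small-sample corrected and ignores the strata. With the uncorrected one, HADS coverage is 91.9 to 93.5% without the stratum, and adding the stratum lowers it in every scenario. This stands, and it is why the two changes belong together. A reader might infer that this trial's intervals will be conservative, or that they will under-cover. The documents support neither, since the variance method may be fixed in the cited paper.

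Second, HADS, the one outcome with a power calculation, gains essentially nothing, and no gain is shown for the Hypothesis 2b outcomes, which all have baseline scores. This also stands.

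Third, a short pre-specified covariate list is defensible at 27 per arm, and the plan shows concern about overfitting under Hypothesis 2a, where it caps models at four covariates. Adding the stratum gives at most four (age, gender, baseline outcome, stratum). That cap was set for a pooled model of 54 patients, so it is only a loose guide for models fitted per arm. The argument would justify the omission if the plan made it; the plan does not.

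A reader might also infer bias or inflated type I error from the omission. Neither follows: stratified allocation balances the factor, and omission by itself only widens the reported interval.

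**Conclusion.** The point holds as a minor one. The trial stratifies by a factor that its pre-specified outcome and propensity models leave out without a reason. The estimate is valid and its true precision is essentially unchanged; only reported uncertainty is affected, and only for secondary outcomes.

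Under the stated assumptions and a corrected standard error that ignores the strata, a history effect of 0 to 0.6 SD gives a negligible width change for HADS and about -1% to +4% where there is no baseline measure. The +10.6% at 1.0 SD should not be read as the likely loss. It is an upper bound that the documents do not support, as they give neither the prevalence nor the prognostic strength of history. If the standard error is uncorrected, the larger problem is the opposite one, intervals that are mostly too narrow, and adding the stratum alone would not help.

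**What to change.** In Section 7c, Hypothesis 1b:

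1. State the variance method, with a degrees-of-freedom correction and a t reference distribution. Do not add the stratum with an uncorrected standard error.
2. Add history of depression, as used at randomisation, to the outcome regression and propensity models, keeping age, gender and the baseline outcome. The benefit is mainly for outcomes with no baseline measure. Carry it to Hypothesis 2b for consistency only.
3. State that the term is omitted if a stratum is nearly empty in an arm.
4. If the stratum is left out on purpose, give the reason.

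Leave the drop-out model as it is. It already has six or more covariates per arm (age, gender, HADS, Brief Cope, CD RISC, BADS) for at most about four missing outcomes per arm: 0.15 × 27 = 4.05. That is a ceiling, not an expectation. The plan's figure is below 15% and includes deaths, which Hypothesis 1b excludes by analysing 12-week survivors.

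The cost is a short edit and no new data, since the stratum is known for every randomised patient. It adds one parameter per model (per arm in the outcome regression), or about 1% in CI width (0.8% in these runs) if history is not prognostic.
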